10.1.5.3 All Subjects entering the Extension Treatment Period

All AEs occurring on or after study start (i.e., signing of informed consent) and up to 30 days after study treatment discontinuation must be recorded on specific AE pages of the eCRF.

10.1.6 Follow-up of adverse events

AEs still ongoing more than 30 days after study treatment discontinuation must be followed up until they are no longer considered clinically relevant.

Confidential

10.2 Serious adverse events

10.2.1 Definitions of serious adverse events

10.2.1.1 Serious adverse events

An SAE is defined by the ICH guidelines as any AE fulfilling at least one of the following criteria:

- Fatal.
- Life-threatening: refers to an event in which the subject was at risk of death at the time of the event. It does not refer to an event that hypothetically might have caused death had it been more severe.
- Requiring inpatient hospitalization, or prolongation of existing hospitalization.
- Resulting in persistent or significant disability or incapacity.
- Congenital anomaly or birth defect.
- Medically significant: refers to important medical events that may not immediately result in death, be life-threatening, or require hospitalization but may be considered to be SAEs when – based upon appropriate medical judgment – they may jeopardize the subject and may require medical or surgical intervention to prevent one of the outcomes listed in the definitions above.

The following reasons for hospitalization are exempted from being reported:

- Hospitalization for cosmetic elective surgery, or social and/or convenience reasons.
- Hospitalization for pre-planned (i.e., planned prior to signing informed consent) surgery or standard monitoring of a pre-existing disease or medical condition that did not worsen, e.g., hospitalization for coronary angiography in a subject with stable angina pectoris.

However, complications that occur during hospitalization are AEs or SAEs (for example if a complication prolongs hospitalization).

10.2.1.2 Serious adverse events associated with the study design or protocol-mandated procedures

An SAE is defined as related to study design or protocol-mandated procedures if it appears to have a reasonable possibility of a causal relationship to either the study design or to protocol-mandated procedures. Examples include discontinuation of a subject's previous treatment during a washout period leading to exacerbation of the underlying disease or a complication of an invasive procedure that is specifically required by the protocol.

Confidential

10.2.2 Reporting of serious adverse events

10.2.2.1 During screening period

All SAEs that occur after study start (i.e., signing of informed consent) must be reported (whether considered associated or not associated with study design or study-mandated procedures).

These SAEs must be reported on an SAE form and also in the eCRF.

10.2.2.2 During Core Treatment Period and Extension Treatment Period

All SAEs, regardless of investigator-attributed causal relationship, must be reported.

These SAEs must be reported on an SAE form and also on the AE pages in the eCRF.

10.2.2.3 During the follow-up period for subjects prematurely discontinued from the Core Treatment Period

All SAEs, regardless of investigator-attributed causal relationship, which occur during the follow-up period up to 30 days after study treatment discontinuation must be reported on AE pages in the eCRF and on an SAE form.

10.2.2.4 During follow-up period for subjects not prematurely discontinued from the Core Treatment Period and not entering the Extension Treatment Period

All SAEs, regardless of investigator-attributed causal relationship, which occur during the follow-up period up to 90 days after study treatment discontinuation must be reported on AE pages in the eCRF and on an SAE form.

10.2.2.5 During follow-up period for all subjects entering the Extension Treatment Period

All SAEs, regardless of investigator-attributed causal relationship, which occur during the follow-up period up to 30 days after study treatment discontinuation must be reported on AE pages in the eCRF and on an SAE form.

10.2.3 Follow-up of serious adverse events

SAEs still ongoing at the EOS visit must be followed up until resolution or stabilization, or until the event outcome is provided, e.g., death.

10.2.4 After the follow-up period

New SAEs occurring after the follow-up period must be reported to the Actelion drug safety department within 24 hours of the investigator's knowledge of the event, **only** if considered causally related to previous exposure to the study treatment by the investigator.

Confidential

10.2.5 Reporting procedures

All SAEs must be reported by the investigator to the Actelion drug safety department within 24 hours of the investigator's first knowledge of the event.

All SAEs must be recorded on an SAE form, irrespective of the study treatment received by the subject, and whether or not this event is considered by the investigator to be related to study treatment.

The SAE forms must be faxed to the Actelion drug safety department (contact details are provided on the SAE form). The investigator must complete the SAE form in English and must assess the causal relationship of the event to study treatment.

Follow-up information about a previously reported SAE must also be reported within 24 hours of receiving it. The Actelion drug safety department may contact the investigator to obtain further information.

If the subject is hospitalized in a hospital other than the study site, it is the investigator's responsibility to contact this hospital to obtain all SAE-relevant information and documentation.

The reference safety document to assess expectedness of a suspect serious adverse reaction and reported by the sponsor to health authorities, ECs/IRBs and investigators is the reference safety information section of the Investigator's Brochure [Ponesimod IB].

The SAEs listed below are commonly seen with the underlying disease and are therefore expected to occur in this subject population. These SAEs will be treated as "disease-related" and expected (unless fatal) and will therefore not require expedited reporting to health authorities, IRBs/IECs, and investigators. However, these events will be monitored during the study by the sponsor and by the Study Monitoring Committee:

- Relapses of the underlying leukemia and complications.

10.3 Pregnancy

If a woman becomes pregnant while on study treatment, study treatment must be discontinued. The investigator must counsel the subject and discuss the risks of continuing with the pregnancy and the possible effects on the fetus.

10.3.1 Reporting of pregnancy

Irrespective of the treatment received by the subject, any pregnancy occurring during the study including during the 30 days following study treatment discontinuation must be reported within 24 hours of the investigator's knowledge of the event.

Confidential

Pregnancies must be reported on the Actelion Pregnancy form, which is faxed to the Actelion drug safety department (see contact details provided on the Actelion Pregnancy form), and on an AE page in the eCRF.

Male contraception

Nonclinical studies have shown no evidence of an effect on male reproductive organs during the administration of ponesimod. It is considered very unlikely that a significant dose of ponesimod would be delivered to the female by seminal transfer and the potential risk of harm to a human fetus is considered to be very small, based on the high safety margins of 1730 to 1920 for estimated exposure to ponesimod potentially achieved in human females via seminal fluid transfer. Therefore, there is no specific recommendation for male contraception. (Note: For allowed concomitant therapies during this trial that require male contraception, the respective method of contraception must be applied.)

10.3.2 Follow-up of pregnancy

Any pregnancy must be followed to its conclusion and its outcome must be reported to the Actelion drug safety department.

Any AE associated with the pregnancy occurring during the follow-up period after study drug discontinuation must be reported on separate AE pages in the eCRF. Any SAE occurring during pregnancy must be reported on an SAE form as described in Section 10.3.1.

10.4 Study safety monitoring

Clinical study safety information (AEs, SAEs, laboratory values, ECGs, vital signs, and project-specific labs/examinations as required) is monitored and reviewed on a continuous basis by the Actelion clinical team (in charge of ensuring subjects' safety as well as data quality) by periodically monitoring clinical studies' activities from protocol conception to database closure. In addition, an SMC is monitoring safety data [see Section 3.5].

11 STATISTICAL METHODS

All statistical analyses will be conducted by Actelion or by designated contract research organizations supervised by Actelion.

The Statistical Analysis Plan (SAP) will be approved prior to database lock for the final analyses. The SAP provides the full details of all analyses, data displays, and algorithms to be used for data derivations.

All data will be listed, and endpoints will be summarized by appropriate descriptive statistics (tables or figures), typically including:

- Number of non-missing observations, number of missing observations, mean, standard deviation (STD), median, Q1, Q3, minimum and maximum for continuous endpoints;
- Number of non-missing observations, number of missing observations and frequency with percentage per category (percentages based on the number of non-missing observations) for categorical endpoints;
- Number of subjects at risk, cumulative number of events, cumulative number of censored observations and Kaplan-Meier estimates of the survival function for time-to-event endpoints.

Absolute changes from baseline are defined as: post-baseline value minus baseline value, i.e., a positive sign indicates an increase as compared to baseline.

A percentage (relative) change from baseline is defined as the absolute change from baseline divided by the baseline value (if the baseline value not equal 0) multiplied by 100.

11.1 Analysis sets

11.1.1 Screened analysis set

This analysis set includes all subjects who were screened and received a subject number.

11.1.2 Full analysis set

The Full analysis set (FAS) includes all subjects who received at least one dose of study medication.

11.1.3 Per-protocol set

The Per-protocol set (PPS) is defined as subjects from the FAS without any major protocol deviations. The most important protocol deviations include:

- Subject failing to reach the Week 24 assessment, i.e., by discontinuing treatment early or for any other reason than lack of efficacy or death
- Subject withdrawing consent before the Week 24 assessment

Confidential

- Subjects not adhering to the treatment regimen (mandatory concomitant medication, up-titration, study drug)
- Subject receiving prohibited concomitant therapy
- Start of any other IS systemic therapies during the course of the trial

Additional details of the definition of the PPS will be described in the SAP.

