PERIODS	Screening period 
• This period lasts up to 30 days prior to the day final eligibility is established and includes the screening visit and all baseline assessments. Core Treatment Period 
• The Core Treatment Period starts at the time of first intake of study drug, and continues until the end of treatment at Week 24.• Visits during the Core Treatment Period consists of an enrollment visit (Day 1) and visits at Weeks 4, 8, 12, 16, 20, and 24.• The End-of-Treatment 1 (EOT1) visit takes place at Week 24, or earlier in case of premature discontinuation of study drug. In all cases, the EOT1 visit should take place not later than 7 days after the last dose of study drug.• All subjects will be treated according to local standard of care at investigator's discretion after EOT1. Core Safety Follow-up Period 1

Confidential

- All subjects will enter the core safety follow-up period after EOT1.
- The follow-up period for subjects who were prematurely discontinued lasts for 30 days after the last dose of study drug and ends with the 30-day follow-up 1 (FU1) visit, which is also the End-of-Study (EOS) visit.
- The follow-up period for subjects who were not prematurely discontinued lasts for 90 days after the last dose of study drug, and consists of the 30-day FU1 site visit and the 90-day follow-up 2 (FU2) visit, which is also the EOS visit. FU1 and FU2 are cancelled if the subject enrolls in Extension Treatment and visit EX-1 (Extension visit 1) occurs the day of or prior to the scheduled FU1 visit. FU2 is cancelled if the subject enrolls in Extension Treatment and visit EX-1 occurs the day of or prior to the scheduled FU2 visit.

Extension Treatment Period

- Subjects who were not prematurely discontinued from the Core Treatment Period, and whose chronic GVHD was assessed by National Institutes of Health (NIH) response criteria to have progressed versus EOT1 disease activity, may be restarted on study drug and enter the Extension Treatment Period. The assessment of progression and the re-initiation of ponesimod must both occur at least 7 days after EOT1 and no later than 90 days after EOT1. (Note: subjects must not have been started on immunosuppressant (IS) therapy other than agents used during the Core Treatment Period).

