6.3.4 Other efficacy endpoints

Other efficacy endpoints include:

- Need for rescue therapy for chronic GVHD
 - Rescue therapy is the addition of any new systemic or topical IS therapy, or exceeding baseline dose for any non-steroid IS, or exceeding glucocorticoid dose equivalent to prednisone > 1 mg/kg/day
- Partial or complete organ-specific response for the specific organ manifestation at Week 12 and Week 24 in subjects with a specific organ manifestation of chronic GVHD at study baseline
 - Affected organs limited to 2014 NIH consensus criteria organs of skin, eyes, mouth, esophagus, upper GI, lower GI, liver, lungs, and joints and fascia
- Partial or complete overall response at 12 weeks post-enrollment
- Complete response at Week 24
- Partial or complete overall response at latest evaluable assessment during the core study (Week 12 and Week 24)
- Average glucocorticoid daily dose over 24 weeks versus baseline dose
- Percent glucocorticoid dose at Week 24 versus baseline

Confidential

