11.2.8 Analysis of the efficacy variables

The analyses of all exploratory endpoints will be based on the PPS and FAS, if applicable. The following binary endpoints will be summarized descriptively as described in Section 11:

- Achievement of a partial or complete overall response at 24 weeks (per NIH Consensus Development Project response criteria)
- Need for rescue therapy for chronic GVHD
- Partial or complete organ-specific response for the specific organ manifestation at Week 12 and Week 24 in subjects with a specific organ manifestation of chronic GVHD
- Partial or complete overall response at Week 12
- Complete response at Week 24
- Partial or complete overall response at latest evaluable assessment during the core study (Week 12 and Week 24)

The remaining two exposure-related, continuous endpoints will be analyzed based on summary statistics as described in Section 11:

- Average glucocorticoid daily dose over 24 weeks versus baseline dose
- Percent glucocorticoid dose at Week 24 versus baseline

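### Starting a new systemic immunosuppressant removes a subject from the per-protocol set, so the per-protocol analysis of need for rescue cannot count that rescue, and per-protocol response is probably too high

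*Combined protocol and SAP*

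**What the plan says.** Section 11.1.3 defines the PPS as FAS subjects without major protocol deviations and lists the most important ones. Three matter here:

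- The last bullet: "Start of any other IS systemic therapies during the course of the trial".
- The first bullet: "Subject failing to reach the Week 24 assessment, i.e., by discontinuing treatment early or for any other reason than lack of efficacy or death".
- A bullet on receiving prohibited concomitant therapy. Section 5.3.5 forbids immunosuppressants other than those prescribed per protocol, so this bullet can reach the same subjects.

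The section closes with: "Additional details of the definition of the PPS will be described in the SAP".

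Section 6.3.4 defines the rescue endpoint: "Rescue therapy is the addition of any new systemic or topical IS therapy". Raising a non-steroid immunosuppressant above its baseline dose, or a glucocorticoid above 1 mg/kg/day prednisone-equivalent, also counts. Section 11.2.3 repeats this and scores anyone who leaves the study before the Week 24 assessment as a non-responder, both for Week 24 response and for the rescue endpoint.

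Section 11.2.8 states: "The analyses of all exploratory endpoints will be based on the PPS and FAS, if applicable". Its list of binary endpoints includes Week 24 overall response and "Need for rescue therapy for chronic GVHD". The Synopsis (Statistical methodology) makes the FAS the main set for these endpoints, with some analyses repeated on the PPS, all of them descriptive.

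**The concern.** A per-protocol set should be defined by how the trial was conducted, not by how the subject fared. Here one event, the start of a new systemic immunosuppressant, is both an endpoint failure and a reason to leave the set on which that endpoint is analysed.

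This applies even to a subject handled as the protocol asks. Section 5.1.10 says that ponesimod should be stopped before rescue immunosuppression begins in the Core Treatment Period. A subject who does so has followed the protocol and has a treatment outcome, yet is classed as a major deviator.

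The bullets also pull against each other. The first appears to keep subjects who stop for lack of efficacy. The last removes those same subjects once they start another systemic agent.

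At stake is how two descriptive PPS results are read in a single-arm trial of 30 subjects: a rescue rate that omits its main kind of event, and a response rate with some of the failures taken out of the denominator.

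**Working it through.** The plan gives no figure for response, rescue or PPS size, so there is none to reproduce. Its power figures (about 85% with 30 subjects, 75% with 23) concern lymphocyte counts and do not enter here.

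**Step 1: the text.**

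| Event before Week 24 | Rescue endpoint (6.3.4, 11.2.3) | PPS (11.1.3) |
|---|---|---|
| New systemic immunosuppressant | Failure | Removed |
| Background immunosuppressant raised above the limit | Failure | Probably removed, as regimen non-adherence |
| Topical-only rescue | Failure | No bullet clearly removes it |
| Adverse-event stop or withdrawn consent, leaving the study | Scored as failure | Removed |
| Stop for lack of efficacy, no new systemic agent | Scored as failure if the study is left | Kept, if the first bullet's exception is read that way |

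The first row is enough for the downward bias in the rescue rate. It needs no assumed numbers beyond at least one such event.

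**Step 2: inputs for an illustration.** N = 30 is the planned sample size. All other counts are assumptions: R = 12 responders; s systemic rescues and o other early stops, all FAS non-responders and all removed from the PPS; one topical-only rescue and one lack-of-efficacy stop, kept in both sets.

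**Step 3: formulas.**
- FAS response = R/30; PPS response = R/(30 − s − o).
- FAS rescue-endpoint failure = (s + o + 2)/30; PPS failure = 2/(30 − s − o).

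**Step 4: results.**

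| s, o | Response FAS | Response PPS | Failure FAS | Failure PPS |
|---|---|---|---|---|
| 0, 0 | 12/30 = 40.0% | 12/30 = 40.0% | 2/30 = 6.7% | 2/30 = 6.7% |
| 3, 0 | 40.0% | 12/27 = 44.4% | 5/30 = 16.7% | 2/27 = 7.4% |
| 6, 0 | 40.0% | 12/24 = 50.0% | 8/30 = 26.7% | 2/24 = 8.3% |
| 3, 3 | 40.0% | 12/24 = 50.0% | 8/30 = 26.7% | 2/24 = 8.3% |
| 6, 3 | 40.0% | 12/21 = 57.1% | 11/30 = 36.7% | 2/21 = 9.5% |

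With 3 to 6 systemic rescues and 3 other stops, PPS response is 10.0 to 17.1 points above FAS. The rows with o = 0 show the systemic-rescue exclusion alone: 4.4 to 10.0 points. With R = 9 and o = 3, the gaps are 37.5 − 30.0 = 7.5 and 42.9 − 30.0 = 12.9 points.

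**Step 5: when the direction for response would reverse.** If k subjects are removed and j of them are responders, PPS response is (R − j)/(30 − k). This exceeds R/30 only when j/k < R/30. With R = 12 and k = 9 the limit is 0.40 × 9 = 3.6: three responders removed gives 9/21 = 42.9% (still above 40.0%), four gives 8/21 = 38.1% (below). The upward bias therefore depends on most removed subjects being non-responders. That is likely, because early stoppers have their end-of-study visit 30 days after the last dose (3.2.3), so most leave before Week 24 and are scored as non-responders. It is not certain.

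**The case against.** The strongest reply is that little depends on the PPS. Efficacy is exploratory, the FAS is the main set, the summaries are descriptive, and the primary analysis is of lymphocyte counts on the PD analysis set. The words *if applicable* in section 11.2.8 would let the sponsor report rescue on the FAS alone, and details of the PPS are left to the SAP. The first part stands and limits the consequence. The second does not remove the problem: section 11.2.8 names need for rescue in its list, and the bullet in 11.1.3 is already written. The deferral only makes the repair easy.

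Four stronger readings may tempt a reader, and the documents do not support them.

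- *The PPS excludes the treatment failures.* Stable, mixed or progressing disease at Week 24 stays, and so does topical-only rescue. In the illustration with s = 6 and o = 3, 9 of the 21 PPS subjects are non-responders.
- *The PPS rescue rate is zero by construction.* Only the new-systemic component is forced to zero. The endpoint has other components, and the illustration leaves 8 to 10%.
- *Completers who receive later care are deleted.* The Synopsis (Periods) says: "All subjects will be treated according to local standard of care at investigator's discretion after EOT1". The last PPS bullet has no explicit time limit, so this reading is possible. But section 5.2, which covers the Core Treatment Period only, speaks of the course of the study when it means that period, so the reading is not established. Such exclusions could also remove responders.
- *The PPS and FAS results are meant to corroborate each other.* Nothing in the documents says so; the Synopsis makes the PPS subordinate.

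**Conclusion.** The point holds in a limited form. As written, new systemic rescue cannot appear in the PPS analysis of need for rescue, and that rate is biased downward. This follows from the text alone. PPS Week 24 response is probably biased upward; both direction and size depend on who is removed. The figure of about 10 to 17 points rests on assumed counts (12 responders, 3 to 6 systemic rescues, 3 other early stops, none of those removed a responder). With no such events the two sets agree. The effect is confined to a secondary set for exploratory, descriptive endpoints.

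Two wordings need attention whatever the size. The first bullet can be read as removing every early discontinuation, which would cancel its own exception. Section 5.2.2 allows systemic glucocorticoids to be initiated for a flare or another condition with ponesimod continuing. Such a start also fits the addition of a new systemic agent in the rescue definition, and possibly the last PPS bullet. These passages must be reconciled.

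**What to change.** 1. In section 11.2.8, analyse need for rescue therapy on the FAS only.
2. In section 11.1.3, limit the last bullet to systemic immunosuppressants started before the Week 24 assessment, while on ponesimod and in breach of the protocol.
3. State that rescue started after ponesimod is stopped is an outcome scored as failure, not a deviation. Apply this to the last bullet, the prohibited-therapy bullet and the first bullet together; otherwise one of the others still removes the same subject.
4. Reword the first bullet so that its exception for lack of efficacy or death can be read only one way.
5. Reconcile the PPS and rescue definitions with the glucocorticoid provision in section 5.2.2.

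The cost is wording only, with no new data and no change to the sample size. The PPS becomes larger and its rates probably less favourable. In the illustration with s = 6 and o = 3, keeping the systemic rescues takes the PPS from 21 to 30 − 3 = 27 subjects and its response rate from 57.1% to 12/27 = 44.4%. The remaining gap to 40.0% comes from the other early stops, which the PPS would still exclude.
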